6.1 Analysis Sets

Subjects will be analyzed per the randomized treatment groups they were assigned to in the previous DACAB study.

6.1.1 Full Analysis Set (FAS)

The Full Analysis Set (FAS) in current study is same as FAS in DACAB trial.

6.1.2 Per-protocol Set (PPS)

Per-protocol set (PPS) is defined as all subjects in the FAS with exclusion of the following subjects:

- Subject discontinued the application of study drug longer than 60 days during the treatment phase in the previous DACAB study

PPS will only be used in the analysis of primary observational endpoint.

The analysis using the FAS will be regarded as primary while the analysis based on PPS will act as supportive.

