Statistical Analysis Plan

DACAB Trial: Follow-up Extension

(DACAB-FE)

NCT03987373

V 1.0 (2021/6/5)

[name], Doctor
Senior Statistician
Department of Biostatistics
School of Public Health
Fudan University

Date

Table of Contents

1. Background	1
2. Study Objectives	2
3. Study Design	3
4. Evaluation Indicators	4
4.1 Primary Outcome	4
4.2 Secondary Outcome	4
4.3 Evaluation and Calculation of Endpoints	5
5. Subject Selection Criteria	6
6. Statistical Analysis	6
6.1 Analysis Sets	6
6.1.1 Full Analysis Set (FAS)	6
6.1.2 Per-protocol Set (PPS)	6
6.2 Methods of Statistical Analyses	6
6.2.1 General Method of Analysis	6
6.2.2 Demographics and Baseline Characteristics	7
6.2.3 Primary Outcome	7
6.2.4 Secondary Outcome	7
6.2.5 Laboratory Indicators	8
6.2.6 Bleeding Events	8
6.2.7 Safety Events	8
6.2.8 Concomitant medications	8
6.2.9 Graft vessels cohorts	8
6.2.10 Subgroup analysis and exploratory analysis on subgroup cohorts	8
6.2.11 Data Transformation	9

6.3 Sample Size	9
7. Results of Statistical Analysis	10
 7.1 Primary and secondary objectives	10
 7.1.1 Enrollment and Baseline characteristics	10
 7.1.2 Primary Outcome	19
 7.1.3 Secondary Outcomes	21
 7.1.4 Laboratory examination during follow-up	30
 7.1.5 Concomitant medications and bleeding events	31
 7.1.6 Subgroup analysis	32
 7.2 Exploratory Objectives	35
 7.2.1 Baseline characteristics	35
 7.2.2 Major clinical events	42
7.3 Supplementary tables	46

1. *Background*

DACAB trial is an open label multi-center randomized clinical trial. The patients enrolled in DACAB trial were randomly assigned to the (1) ticagrelor+aspirin (T+A) group, (2) ticagrelor(T) group and (3) aspirin (A) group. Patients were treated and followed up for 12 months. The primary endpoint was the patency rate of saphenous vein graft (SVG) after 1 year of CABG. Secondary endpoint included MACEs within 1 year after CABG.

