There are 500 patients were enrolled from July 2014 through November 2015 and follow-up was completed in January 2017, 168 patients in the T+A group, 166 in T group and 166 in A group. The results showed that the 1-year SVG patency rate (primary endpoint) of T+A group was 88.7% (432/487, T+A vs A, p=0.0006), the T group was 82.8% (371/485, T vs A, p=0.0962), and the A group was 76.5% (404/488). The incidence of MACE during 1 year of follow-up was 1.8% in T+A group, 2.4% in T group, and 5.4% in A group. The DACAB trial demonstrated that compared with aspirin monotherapy, the combination of ticagrelor and aspirin significantly improved 1-year SVG patency after CABG. Meanwhile, the combination of ticagrelor and aspirin therapy or ticagrelor monotherapy showed a favor trend with reducing the MACEs compared with aspirin monotherapy.

Would the observed differences in SVG patency at 1 year post CAGB translate into long-term clinical benefit? This remain to be a great interest to follow up these patients. Therefore, in present study, we intend to collect and analyze the long-term data in patients who were enrolled and survived in DACAB trial. We would observe the clinical outcomes of these subjects at 5-year post-CABG.

2. Study Objectives

- Primary Objective**

The primary objective is to compare the incidence of major adverse clinical events-4 (MACE-4, a composite of all-cause death, myocardial infarction, stroke, and coronary revascularization) among 3 randomized regimens in previous DACAB trial in the extended five-year follow-up after CABG.

- Secondary Objectives**

The secondary objectives are to compare the incidence of MACE-5 (a composite of all-cause death, myocardial infarction, stroke, coronary revascularization and hospitalization for unstable angina); MACE-3 (a composite of cardiovascular death, myocardial infarction and stroke); all-cause death; cardiovascular death; myocardial infarction; stroke; coronary revascularization; hospitalization for unstable angina and graft failure among 3 randomized regimens in previous DACAB trial in the five-year follow-up after CABG.

- Exploratory Objectives**

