4.1 Primary Outcome

MACE-4, defined as a composite of all-cause death, myocardial infarction, stroke, and coronary revascularization. The outcome measure is the time to the first occurrence of MACE-4 event from randomization to the last visit.

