7.1 Primary and secondary objectives

7.1.1 Enrollment and Baseline characteristics

Table 1 Analysis sets

Center	ITT				FAS				PPS			
	A	A+T	T	Total	A	A+T	T	Total	A	A+T	T	Total
1												
2												
3												
4												
5												
Total												

Table 2 Subjects not included in PPS

Random number	Group

Reason: Subjects in the DACAB study who stopped the study drug for more than 60 days.

Table 3 Demographic and baseline characteristics (FAS)

Indicator	A	T+A	T	P
Age				0.***
N(missing)	*** (***)	*** (***)	*** (***)	
mean(sd)	*** (***)	*** (***)	*** (***)	
median	***	***	***	
Min-Max	***~***	***~***	***~***	
p25-p75	***~***	***~***	***~***	
Sex				0.***
N(missing)	*** (***)	*** (***)	*** (***)	
Male	*** (***)	*** (***)	*** (***)	
Female	*** (***)	*** (***)	*** (***)	
Height				
N(missing)	*** (***)	*** (***)	*** (***)	
mean(sd)	*** (***)	*** (***)	*** (***)	
median	***	***	***	
Min-Max	***~***	***~***	***~***	
p25-p75	***~***	***~***	***~***	
Weight				0.***
N(missing)	*** (***)	*** (***)	*** (***)	
mean(sd)	*** (***)	*** (***)	*** (***)	
median	***	***	***	
Min-Max	***~***	***~***	***~***	
p25-p75	***~***	***~***	***~***	
BMI				0.***

Indicator	A	T+A	T	P
N(missing)	*** (***)	*** (***)	*** (***)	
mean(sd)	*** (***)	*** (***)	*** (***)	
median	***	***	***	
Min-Max	***~***	***~***	***~***	
p25-p75	***~***	***~***	***~***	
Clinical status				0.***
N(missing)	*** (***)	*** (***)	*** (***)	
Stable angina	*** (***)	*** (***)	*** (***)	
Unstable angina	*** (***)	*** (***)	*** (***)	
Non - ST-elevation myocardial infarction	*** (***)	*** (***)	*** (***)	
History of myocardial infarction				0.***
N(missing)	*** (***)	*** (***)	*** (***)	
Yes	*** (***)	*** (***)	*** (***)	
No	*** (***)	*** (***)	*** (***)	
Time since onset of myocardial infarction (day)				0.***
N(missing)	*** (***)	*** (***)	*** (***)	
<21	*** (***)	*** (***)	*** (***)	
21-90	*** (***)	*** (***)	*** (***)	
>90	*** (***)	*** (***)	*** (***)	
CCS class				0.***

Indicator	A	T+A	T	P
N(missing)	*** (***)	*** (***)	*** (***)	
0	*** (***)	*** (***)	*** (***)	
I	*** (***)	*** (***)	*** (***)	
II	*** (***)	*** (***)	*** (***)	
III	*** (***)	*** (***)	*** (***)	
IV	*** (***)	*** (***)	*** (***)	
NYHA class				0.***
N(missing)	*** (***)	*** (***)	*** (***)	
I	*** (***)	*** (***)	*** (***)	
II	*** (***)	*** (***)	*** (***)	
III	*** (***)	*** (***)	*** (***)	

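### The per-protocol rule ignores whether a drug stop came before or after a first MACE-4 event, so it can remove adherent subjects together with their primary event

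*SAP*

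**What the plan says.** SAP 6.1.2 and protocol 9.1.2 define the PPS as the full analysis set (FAS) minus one class of subject: "Subject discontinued the application of study drug longer than 60 days during the treatment phase in the previous DACAB study". The shell of Table 2 in SAP 7.1.1 lists excluded subjects by random number and group under a single preset reason: "Reason: Subjects in the DACAB study who stopped the study drug for more than 60 days". It has no place for the date of the stop, its cause, or an earlier endpoint event.

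The role of the PPS is limited. SAP 6.1.2 states "PPS will only be used in the analysis of primary observational endpoint" and "The analysis using the FAS will be regarded as primary while the analysis based on PPS will act as supportive". The output is Tables 7 and 8 (event rates, hazard ratios and log-rank tests for MACE-4).

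Two further statements fix the time windows. On treatment, SAP Background says "Patients were treated and followed up for 12 months". On the endpoint, SAP 4.1 says "The outcome measure is the time to the first occurrence of MACE-4 event from randomization to the last visit". Neither document says how a subject who died in year 1 is classed for the PPS.

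**The concern.** The window in which a subject can be excluded (the 12-month treatment phase) lies inside the window in which MACE-4 is counted (from randomization). A subject who took the assigned drug until a myocardial infarction, stroke or revascularization and then stopped for more than 60 days was adherent for all the time that matters to a first-event analysis. The rule as written removes that subject, and the event goes too. Membership of the set can then depend on the outcome and not only on adherence.

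The DACAB year-1 event rates differ by arm, so losses of this kind need not balance. A PPS hazard ratio that differs from the FAS could be read as a sign that the result is fragile when the difference comes from the set definition. The planned Table 2 would not show which explanation applies.

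**Working it through.** **Inputs from the documents**
- Arm sizes (SAP 6.3): T+A 168, T 166, A 166.
- Year-1 MACE (SAP Background): "The incidence of MACE during 1 year of follow-up was 1.8% in T+A group, 2.4% in T group, and 5.4% in A group".
- Treatment phase 12 months; 1 year = 365.25 days (SAP 6.2.11).

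**Assumptions, not in the documents**
- DACAB MACE stands in for MACE-4 in year 1.
- The same share q of year-1 event subjects stops and is excluded in each arm.
- The hazard in A after year 1 is 4% per year (range 2–6%), and the later T+A versus A hazard ratio is 1.0, 0.8 or 0.65.

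**Step 1. Reproduce the stated rates.** 3/168 = 1.79%, 4/166 = 2.41%, 9/166 = 5.42%. No other whole counts round to the stated figures. The year-1 T+A minus A difference is −3.6 points and the ratio is 0.33.

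**Step 2. Which events can be lost.** A stop can exceed 60 days within the phase only if it begins before day 365.25 − 60 = 305.25. If events are spread evenly, 305.25/365.25 = 0.836 of year-1 events are exposed: about 9 × 0.836 = 7.5 in A and 3 × 0.836 = 2.5 in T+A. No event in years 2–5 can be lost this way.

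**Step 3. Year-1 effect.** An equal share q removes 9q − 3q = 6q more events from A than from T+A. At q = 0.5:
- A: 4.5/161.5 = 2.79%
- T+A: 1.5/166.5 = 0.90%
- difference: −1.9 points

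The year-1 ratio stays near one third (0.32). What falls is the weight of year 1, so the five-year hazard ratio drifts towards the later one. In every scenario below, the later one is nearer 1.

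**Step 4. Five-year hazard ratio, closed form.** For arm k with n subjects, e year-1 events and later hazard h, the cumulative hazard is

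H = −ln[1 − (1 − q)e/(n − qe)] + 4h, and HR = H(T+A)/H(A).

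With no later effect (4h = 0.16 in both arms):
- FAS, q = 0: (0.0180 + 0.16)/(0.0557 + 0.16) = 0.83
- PPS, q = 0.836: (0.0030 + 0.16)/(0.0094 + 0.16) = 0.96

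**Step 5. Simulation.** 4,000 log-rank trials per scenario were simulated, with only events before day 305.25 open to exclusion. The full case excludes all of those subjects; the half case excludes half of them.

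| Later HR (A 4%/year) | Closed form, FAS to PPS, full | Simulation, FAS to PPS, full | Simulation, FAS to PPS, half |
|---|---|---|---|
| 1.0 | 0.83 to 0.96 | 0.81 to 0.96 | 0.81 to 0.88 |
| 0.8 | 0.68 to 0.77 | 0.67 to 0.77 | 0.67 to 0.71 |
| 0.65 | 0.57 to 0.63 | 0.57 to 0.64 | 0.57 to 0.59 |

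For a later HR of 0.65, the chance of p < 0.05 falls from about 0.52 to 0.30 in the full case and from about 0.54 to 0.43 in the half case.

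**Range, full case.** At 2% per year (simulation): 0.72 to 0.93, 0.60 to 0.75 and 0.52 to 0.62. At 6% per year (closed form): 0.87 to 0.97, 0.71 to 0.78 and 0.59 to 0.64.

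**The case against.** The strongest reply is that nothing in the documents shows the rule doing harm. A reader might infer that the PPS deletes events unevenly by arm, or that it erases the treatment difference. Neither inference is supported.

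- **No data on stops.** The documents give no number, date or reason for stops, and do not say that endpoint events led to stopping. They support only that the rule can remove events. If the share differed by arm, the direction could differ too.
- **Erasure is a single point.** A hazard ratio of 1.00 requires every year-1 event to be lost and no treatment difference afterwards. Events after about day 305 cannot be lost, and the study asks whether better patency brings long-term benefit. With a later effect, the hazard ratio moves only part of the way.
- **Death as a stop.** Counting a death as a discontinuation is one possible reading, but no text says so. This calls for a clarification and is not evidence of lost events.
- **Proxy.** SAP Background does not give the components of DACAB MACE. MACE-4 here includes any coronary revascularization, and its infarction component includes silent infarction (protocol 5.3.2), so year-1 MACE-4 counts may differ.
- **Limited consequence.** The FAS is primary and no decision rule uses the PPS. With equal shares, the pull on T+A versus A is towards 1, so it would not create a false claim of benefit.

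All of this stands and limits the size of the point. It does not answer the gap itself: the rule has no timing condition, its window overlaps the outcome window, and no other section corrects it.

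**Conclusion.** The point holds as a flaw in the definition of a supportive analysis set. The rule can remove adherent subjects together with their primary event; how many, if any, cannot be learned from the documents. With DACAB MACE as proxy and equal stopping shares, aspirin would lose more events. The supportive T+A versus A hazard ratio would then move towards 1, by 0.15 at most in the 4% per year scenarios (0.81 to 0.96) and by as little as 0.02 at half the share with a later hazard ratio of 0.65. At 2% per year with no later effect, the extreme shift is larger (0.72 to 0.93). These sizes rest on assumed later hazards and assumed stopping shares. The FAS result does not change. The rule should be corrected because the bias is avoidable, but the primary conclusion does not depend on it.

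**What to change.** In SAP 6.1.2 and protocol 9.1.2, exclude only subjects whose interruption of more than 60 days occurred before their first MACE-4 event or death. Days off drug are counted up to that date and no further. Subjects who stopped on or after a first MACE-4 event, or who died on treatment, stay in with the event counted. In Table 2, list the stop date, the reason and whether MACE-4 came first, by arm.

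The cost is one sentence in each document and extra columns in Table 2, using stop and event dates from DACAB. If no event subject is affected, the set does not change.

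There are two downsides:
- Event subjects have a shorter window in which they can be excluded, so they are slightly over-retained. As an illustration, assume 20% of T+A and 10% of A stop independently of events, and half of the stops among event subjects come first. T+A keeps 3 × 0.9 = 2.7 events and 165 × 0.8 = 132 event-free subjects; A keeps 9 × 0.95 = 8.55 and 157 × 0.9 = 141.3. The year-1 ratio becomes (2.7/134.7)/(8.55/149.85) = 0.35, against 0.33 in the FAS.
- Arm differences in stopping before any event can still bias the PPS in either direction. This should be acknowledged when Tables 7 and 8 are interpreted.

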6.2 Methods of Statistical Analyses

6.2.1 General Method of Analysis

Counts and percentages for discrete variables, and mean, SD, maximum, minimum, median, 25th percentiles and 75th percentiles for continuous

variables will be used to summarize data.

The missing data will be assumed missing at random, no imputation will be applied unless specified otherwise.

A 2-sided level of significance of .05 will be applied to all statistical analyses unless specified otherwise. Statistical analyses will be performed using SAS 9.4.

6.2.2 Demographics and Baseline Characteristics

Demographic and baseline characteristic variables will be descriptively summarized by the group in previous DACAB study.

6.2.3 Primary Outcome

Kaplan-Meier will be used to estimate survival curves, and calculate the incidence of major adverse clinical events-4 (MACE4) for each year during the follow-up period. Log-rank test will be used to compare the differences between survival curves. COX regression model will be used to estimate hazard ratios and its 95% confidence intervals.

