### **9.3 Determination of Sample Size**

A total of 500 subjects were randomized in DACAB study (ticagrelor + aspirin, 168; ticagrelor alone, 166; aspirin alone, 166). There are 5 subjects died before 12-month visit, of these, 2 died in ticagrelor + aspirin group, and 3 died in aspirin alone group. Therefore, 495 patients would be scheduled for 5-year on-site visit.

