6.2.10 Subgroup analysis and exploratory analysis on subgroup cohorts

Based on random grouping, planned subgroup analysis will be performed

on gender, age stratification, ACS presentation, hypertension, diabetes mellitus, history of high low-density lipoprotein cholesterol (LDL-C), history of high lipoprotein(a), prior myocardial infarction, stroke, peripheral vascular disease, COPD, history of CKD-3 or higher, smoking, left main coronary artery disease, SYNTAX Score stratification, EuroScore stratification at baseline, on-pump or off-pump, whether to use the internal thoracic artery, complete revascularization or not.

Multivariable analysis, including GLM and propensity score methods, will be applied to exploratory analysis on subgroup cohorts.

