6.3 Sample Size

A total of 500 subjects were randomized in DACAB study (ticagrelor + aspirin, 168; ticagrelor alone, 166; aspirin alone, 166). There were 5 subjects died before 12-month visit, of these, 2 died in ticagrelor + aspirin group, and 3 died in aspirin alone group.

7. Results of Statistical Analysis

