7.1.2 Primary Outcome

Table 5 Occurrence of MACE4 during follow-up (FAS)

Group	Overall occurrence of the event	Event rate during follow-up				
		12 months	24 months	36 months	48 months	60 months
A	*** (***)	**%	**%	**%	**%	**%
T+A	*** (***)	**%	**%	**%	**%	**%
T	*** (***)	**%	**%	**%	**%	**%

Note: Overall occurrence of the event includes all the events during the follow-up period, KM was used to estimate the event rates in different visit.

Table 6 Survival Analysis for MACE4 event during follow-up (FAS)

Group	HR(95% CI)	Logrank P
T+A VS. A	*** (***, ***)	0. ****
T VS. A	*** (***, ***)	0. ****
T+A VS. T	*** (***, ***)	0. ****

Figure 1. Kaplan-Meier curves of MACE4 during the follow-up (FAS)

Table 7 Occurrence of MACE4 during follow-up (PP)

Group	Overall occurrence of the event	Event rate during follow-up				
		12 months	24 months	36 months	48 months	60 months
A	*** (***)	**%	**%	**%	**%	**%
T+A	*** (***)	**%	**%	**%	**%	**%
T	*** (***)	**%	**%	**%	**%	**%

Note: Overall occurrence of the event includes all the events during the follow-up period, KM was used to estimate the event rates in different visit.

Table 8 Survival Analysis for MACE4 event during follow-up (PP)

Group	HR(95% CI)	Logrank P
T+A VS. A	*** (***,***)	0. ****
T VS. A	*** (***,***)	0. ****
T+A VS. T	*** (***,***)	0. ****

Figure 2. Kaplan-Meier curves of MACE4 during the follow-up (PP)

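### The primary MACE-4 analysis names no baseline covariates; a pre-specified adjusted Cox model could add from about 0 to 11 points of power per contrast in a cohort of fixed size

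*SAP*

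**What the plan says.** SAP 6.2.3 gives the whole primary method in three sentences. After the Kaplan-Meier estimates, "Log-rank test will be used to compare the differences between survival curves", and "COX regression model will be used to estimate hazard ratios and its 95% confidence intervals". No covariate, stratum or adjusted model is named, and nothing says that the model is unadjusted. The table shells settle the intention in practice. Tables 6 and 8 give each of the three pairwise contrasts one hazard ratio and one log-rank P, whereas Table 29, for the non-randomised graft-failure cohorts, has a column for an adjusted P. SAP 6.2.4 carries the primary method over to the secondary time-to-event outcomes. Protocol 9.2.3 names only Kaplan-Meier.

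The baseline data are already in the plan. Table 3 tabulates age, diabetes, prior MI, LVEF, SYNTAX score and EuroScore by arm. Most of these are also subgroup factors in SAP 6.2.10, for example "SYNTAX Score stratification, EuroScore stratification at baseline"; LVEF is not on that list.

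The cohort is the one randomised in the parent trial: "ticagrelor + aspirin, 168; ticagrelor alone, 166; aspirin alone, 166". Protocol 9.3 and SAP 6.3 give head counts only, with no power, target hazard ratio or number of events.

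**The concern.** Leaving a prognostic factor out of a Cox model moves the estimated hazard ratio towards 1 and costs power. In most trials a larger sample can make up for that; here recruitment ended with the parent trial. If the tabulated factors do predict MACE-4, adjusting for them gives a more sensitive comparison from data already held.

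Pre-specification is also at stake. Table 3 has a P column for differences between arms, and Protocol 9.2.1 plans to explore how subject characteristics relate to the endpoints. If a chance imbalance appears and the SAP has fixed no adjusted model, any later adjustment will have been chosen after seeing the data, in an open-label trial.

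**Working it through.** **1. The plan's own figure.** 168 + 166 + 166 = 500. Of the five early deaths, "2 died in ticagrelor + aspirin group, and 3 died in aspirin alone group", so 500 − (2 + 3) = 495, which matches "Therefore, 495 patients would be scheduled for 5-year on-site visit". This is a head count; there is no power figure to reproduce.

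**2. Inputs.** From the documents: arm sizes 168 and 166 for T+A against A; five-year follow-up; and "A 2-sided level of significance of .05 will be applied to all statistical analyses unless specified otherwise". Assumed: five-year control MACE-4 rate p of 15-30%, and hazard ratio 0.5-0.7. As a rough anchor for p, holding the one-year MACE rate of 5.4% in arm A (SAP Background) constant for five years gives 1 − 0.946^5 = 0.242, about 24%.

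**3. Unadjusted power.** Expected events D = 166p + 168[1 − (1 − p)^HR]. Power = Φ(√(D·a(1 − a))·|ln HR| − 1.96), with a = 168/334 = 0.503.

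For p = 0.20 and HR = 0.6: D = 33.2 + 168 × 0.1253 = 54.3; √(54.3 × 0.25) × 0.511 − 1.96 = −0.08; power 47%.

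| Control rate | HR 0.5 | HR 0.6 | HR 0.7 |
|---|---|---|---|
| 15% | 57% | 37% | 21% |
| 20% | 70% | 47% | 27% |
| 30% | 86% | 64% | 38% |

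**4. Effect of adjustment.** Simulation: 4,000 trials per scenario, 168 against 166, exponential hazards, censoring at five years only, two-sided 0.05. One baseline score acts on the log-hazard with SD 0.5, 0.75 or 1.0 (hazard ratio 1.65 to 2.72 per SD). The stated hazard ratio is conditional on that score. With no prognostic effect, the simulated log-rank power at 20% and HR 0.6 is 47.2%, in line with step 3.

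| Score SD | Adjusted Cox minus log-rank power, all rates and HRs | At 20%, HR 0.6 |
|---|---|---|
| 0 | −1.4 to −0.4 points | 47.2% to 46.4% |
| 0.5 | −0.5 to +2.6 | 44.0% to 44.9% |
| 0.75 | +1.3 to +6.8 | 41.9% to 45.0% |
| 1.0 | +3.0 to +11.0 | 38.4% to 46.6% |

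The small losses at SD 0 come mainly from comparing a Wald test with a log-rank test: unadjusted Cox power at 20% and HR 0.6 is 46.2%, against 46.4% adjusted. Type I error at a 20% control rate was 4.2-5.1% for all tests. At SD 1.0, 20% and HR 0.6, the average estimate was 0.63 unadjusted and 0.59 adjusted. Monte Carlo error is about 0.8 points per power figure. This is a best case: one complete, correctly specified score and no dropout.

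**5. Missing covariates.** Table 3 has a missing count for nearly every variable, and SAP 6.2.1 plans no imputation unless specified otherwise. Suppose complete-case fitting dropped 10% of subjects (assumed). In step 3, D falls from 54.3 to 48.9 and power from 47% to 43%, a loss of about 4 points that cancels the middle-case gain of 3.

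A simulation with six covariates and five centre strata (HR 0.6, 1,500 runs) shows the same. At a 15% control rate and SD 0.5, 0.8 and 1.0, the gain is +0.3, +2.7 and +3.6 points with complete data, and −2.4, +0.6 and +1.3 with 10% of subjects dropped. At a 25% rate with 10% dropped it is −0.6, +2.1 and +4.9. In a further simulation with six covariates (HR 0.6, control rates 15-25%), adjustment gained about 2 to 11 points, and filling scattered missing values with the mean, with about 10% of subjects affected, kept essentially all of it.

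**The case against.** The case for leaving 6.2.3 alone is a fair one. An unadjusted log-rank test with a Cox hazard ratio is a standard, valid primary analysis of randomised arms, and the plan separates it from the adjusted analyses of non-randomised cohorts. There is no planned power to fall short of. The gain depends on a prognostic strength that the documents do not give, and it can vanish if subjects with missing values are dropped. The SAP is dated 5 June 2021, after the one-year MACE results by arm were published, and follow-up counts from randomisation, so part of the outcome was known. A covariate list chosen then invites the charge that it was informed by outcome.

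Most of this stands and limits the point to efficiency. The missing-data argument applies only to complete-case fitting; SAP 6.2.1 leaves room for a specified rule. The timing argument calls for a list justified without outcome by arm and for keeping the unadjusted result in view. It does not rule adjustment out.

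A reader might infer more than the documents support:

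- That the factors are recorded for every subject. The missing counts in Table 3 provide for the opposite, and completeness is stated nowhere.
- That the factors are known to be strong. No prognostic effect on MACE-4 is quantified.
- That adjustment is the only way to gain power. Fuller event retrieval for subjects lost to follow-up (SAP 4.3), or a different set of contrasts, would also affect it.
- That baseline factors serve only as subgroup splits. Protocol 9.2.1 plans correlations with the endpoints, and SAP 6.2.10 plans multivariable and propensity-score analyses of subgroup cohorts.
- That the unadjusted hazard ratio is biased. The gap between 0.63 and 0.59 reflects a marginal and a conditional hazard ratio, which are different quantities.

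**Conclusion.** The point holds as an efficiency and pre-specification improvement. It is not an error in the plan. The primary analysis is in effect unadjusted, likely prognostic factors are already collected, and the cohort cannot be enlarged.

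Under the assumed ranges, adjustment adds from about 0 to 11 points of power per contrast. In the middle case (20% control rate, HR 0.6, SD 0.75) it adds roughly 3, from 41.9% to 45.0%. The upper end needs both a 30% control rate and an SD of 1.0. Adjustment does not rescue an underpowered contrast: at 20% and HR 0.6, adjusted power is 45-47% at every prognostic SD tried from 0.5 to 1.0. Confidence is high that no covariates are named and low on the exact gain, which also depends on a rule that keeps every subject in the model.

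**What to change.** In SAP 6.2.3, before database lock:

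- Specify a Cox model with arm plus a short fixed list, for example age, diabetes, prior MI, LVEF, EuroScore and SYNTAX score, continuous where available. Record that the list was chosen without reference to outcome by arm.
- Add a simple missing-covariate rule, such as mean fill for continuous values or a missing category, so that no subject is dropped.
- State which analysis is primary. Report the unadjusted log-rank P and hazard ratio alongside, and add the adjusted result to Table 6.
- Use the same model for MACE-5. For MACE-3, which leaves out revascularisation and non-cardiovascular death, use fewer covariates if events are few. As a guide, 54.3 expected MACE-4 events per contrast (20%, HR 0.6) over seven parameters is already only 54.3/7 = 7.8 events per parameter.

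If the sponsor prefers to keep the unadjusted analysis as primary, 6.2.3 should say so and carry the adjusted model as a pre-specified sensitivity analysis.

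The cost is SAP wording, with no new data. The adjusted hazard ratio is conditional on the covariates and should be labelled so. The list would be fixed after the one-year results were published, which the report should disclose. Timing is tight: SAP version 1.0 is dated 5 June 2021 and Protocol 7.4 plans lock in June 2021.
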